### **7.1.1. Electronic Diary**

The subject will be issued an e-diary, based on a smartphone or equivalent technology, and will be asked to monitor and record local reactions, systemic events, and the use of antipyretics/pain medication to treat symptoms for 14 days following vaccination (or 7 days following the first vaccination for subjects on the Day 1, 8, and 30 regimen). The e-diary allows recording of these assessments only within a fixed time window, thus providing the accurate representation of the subject's experience at that time. Data on local reactions, systemic events, and use of antipyretics/pain medication to treat symptoms reported on the e-diary will be transferred electronically to the e-diary vendor, where they will be available for review by investigators and the Pfizer clinicians at all times via an Internet-based portal. E-diary data review is ongoing during subject e-diary data-entry periods (7 days after the first vaccination and 14 days after the second, third, and fourth [if applicable] vaccinations) via an Internet-based portal.

At intervals agreed to by the vendor and Pfizer, these data will be transferred electronically into Pfizer's database for analysis and reporting. These data do not need to be reported by the investigator in the CRF.

Investigators (or designee) will be required to review the e-diary data online at frequent intervals as part of the ongoing safety review.

The investigator or designee must contact the subject in order to obtain stop dates for any ongoing local reactions or systemic events or continuing use of antipyretic/pain medication to treat symptoms on the last day that the e-diary was completed. The stop dates should be documented in the source documents and the information entered in the CRF.

#### **7.1.1.1. Grading Scales**

The grading scales used in this study to assess local reactions and systemic events as described below are derived from the Food and Drug Administration (FDA) Center for Biologics Evaluation and Research (CBER) guidelines on toxicity grading scales for healthy adult volunteers enrolled in preventive vaccine clinical trials.

#### **7.1.1.2. Local Reactions**

During the e-diary reporting period, subjects will be asked to assess redness, swelling, and pain at the injection site and to record the symptoms in the e-diary. If a local reaction persists beyond the end of the e-diary period following vaccination, the subject will be

requested to report that information and any new AEs that develop to the investigator. The investigator will enter this additional information in the CRF.

Redness and swelling will be measured and recorded in measuring device units (range: 1 to 21+), and then categorized during analysis as absent, mild, moderate, or severe based on the grading scale in Table 2. Measuring device units can be converted to centimeters according to the following formula: 1 measuring device unit = 0.5 cm. Pain at the vaccine injection site will be assessed by the subject as absent, mild, moderate, or severe according the grading scale in Table 2.

A subject with a severe local reaction at the injection site will be prompted to contact the investigator to assess the reaction and perform an unscheduled visit as appropriate. Only an investigator or medically qualified person is able to classify a subject's local reaction as Grade 4. If a subject experiences a suspected Grade 4 local reaction, the investigator must immediately notify the sponsor. If a subject experiences a confirmed Grade 3 or 4 local reaction determined to be related to the administration of the investigational product, further vaccinations will be discontinued in that subject.

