**Table 2. Local Reaction Grading Scale**

	Mild (Grade 1)	Moderate (Grade 2)	Severe (Grade 3)	Grade 4
Pain	Does not interfere with activity	Interferes with activity	Prevents daily activity	Emergency room visit or hospitalization
Erythema/ Redness	2.5 cm to 5.0 cm (5 to 10 measuring device units)	>5.0 cm to 10.0 cm (11 to 20 measuring device units)	>10 cm ( $\geq 21$ measuring device units)	Necrosis or exfoliative dermatitis
Induration/ Swelling	2.5 cm to 5.0 cm (5 to 10 measuring device units)	>5.0 cm to 10.0 cm (11 to 20 measuring device units)	>10 cm ( $\geq 21$ measuring device units)	Necrosis

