**Table 3. Systemic Event Grading Scale**

	Mild (Grade 1)	Moderate (Grade 2)	Severe (Grade 3)	Grade 4
Vomiting	1-2 times in 24 hours	>2 times in 24 hours	Requires IV hydration	Emergency room visit or hospitalization for hypotensive shock
Diarrhea	2-3 loose stools in 24 hours	4-5 loose stools in 24 hours	≥6 loose stools in 24 hours	Emergency room visit or hospitalization
Headache	No interference with activity	Some interference with activity	Significant; prevents daily activity	Emergency room visit or hospitalization
Fatigue/ Tiredness	No interference with activity	Some interference with activity	Significant; prevents daily activity	Emergency room visit or hospitalization
New or worsening muscle pain	No interference with activity	Some interference with activity	Significant; prevents daily activity	Emergency room visit or hospitalization
New or worsening joint pain	No interference with activity	Some interference with activity	Significant; prevents daily activity	Emergency room visit or hospitalization

Abbreviation: IV = intravenous.

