## **8. ADVERSE EVENT REPORTING**

### **8.1. Adverse Events**

All observed or volunteered AEs regardless of vaccine group or suspected causal relationship to the investigational product(s) will be reported as described in the following sections.

For all AEs, the investigator must pursue and obtain information adequate both to determine the outcome of the AE and to assess whether it meets the criteria for classification as an SAE requiring immediate notification to Pfizer or its designated representative. For all AEs, sufficient information should be obtained by the investigator to determine the causality of the AE. The investigator is required to assess causality. Follow-up by the investigator may be required until the event or its sequelae resolve or stabilize at a level acceptable to the investigator, and Pfizer concurs with that assessment.

As part of ongoing safety reviews conducted by the sponsor, any nonserious AE that is determined by the sponsor to be serious will be reported by the sponsor as an SAE. To assist in the determination of case seriousness, further information may be requested from the investigator to provide clarity and understanding of the event in the context of the clinical study.

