### **8.6. Serious Adverse Events**

An SAE is any untoward medical occurrence at any dose that:

- Results in death;
- Is life-threatening (immediate risk of death);
- Requires inpatient hospitalization or prolongation of existing hospitalization;
- Results in persistent or significant disability/incapacity (substantial disruption of the ability to conduct normal life functions);
- Results in congenital anomaly/birth defect.
- Lack of efficacy in an approved indication should be reported as an SAE.

Medical and scientific judgment is exercised in determining whether an event is an important medical event. An important medical event may not be immediately life-threatening and/or result in death or hospitalization. However, if it is determined that the event may jeopardize the subject or may require intervention to prevent one of the other AE outcomes, the important medical event should be reported as serious.

Examples of such events are intensive treatment in an emergency room or at home for allergic bronchospasm; blood dyscrasias or convulsions that do not result in hospitalization; or development of drug dependency or drug abuse.

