### 8.9. Severity Assessment

GRADE	If required on the AE CRFs, the investigator will use the adjectives MILD, MODERATE, SEVERE, or LIFE-THREATENING to describe the maximum intensity of the AE. For purposes of consistency, these intensity grades are defined as follows:	
1	MILD	Does not interfere with subject's usual function.
2	MODERATE	Interferes to some extent with subject's usual function.
3	SEVERE	Interferes significantly with subject's usual function.
4	LIFE-THREATENING	Life-threatening consequences; urgent intervention indicated.

Note the distinction between the severity and the seriousness of an AE. A severe event is not necessarily an SAE. For example, a headache may be severe (interferes significantly with the subject's usual function) but would not be classified as serious unless it met one of the criteria for SAEs, listed above.

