#### **Maximum Severity for Local Reactions**

Erythema/redness and induration/swelling are measured and recorded in measuring device units (range: 1-21+) and then categorized as absent, mild, moderate, or severe based on the grading scale in [Table 5](#). Pain at the injection site will be assessed by the subject as absent, mild, moderate, or severe according to the grading scale in [Table 5](#).

For each local reaction, the maximum severity grade of the reaction will be derived for the e-diary collection period (Day 1 to Day 7 after the first vaccination on the Day 1, 8, and 30 regimen, Day 1 to Day 14 after the second and third vaccinations on the Day 1, 8, and 30 regimen, and Day 1 to Day 14 after each vaccination on the Month 0, 1, and 6 regimen) and

after the fourth vaccination of the extension stage in both regimens. The severity grading scale of the local reaction is presented in Table 5.

The maximum severity will be derived as follows:

- = missing, if all values are missing for all days (Day 1 to Day 7 after the first vaccination on the Day 1, 8, and 30 regimen, and Day 1 to Day 14 after all other vaccinations in both regimens).
- = 0, if the subject reports all reactions as “No”, or a combination of missing and “No” for all days (Day 1 to Day 7 after the first vaccination on the Day 1, 8, and 30 regimen, and Day 1 to Day 14 after all other vaccinations in both regimens).
- = highest grade (maximum severity) within 7 days of vaccination after the first vaccination on the Day 1, 8, and 30 regimen, and within 14 days after all other vaccinations in both regimens, if the answer is not “No” for at least 1 day.

Only an investigator or medically qualified person is able to classify a subject’s local reaction as Grade 4. Grade 4 could also be determined if a reaction is reported as an SAE.

Maximum severity of each local reaction on any day (Days 1- X) after **any** vaccination in the originally planned phase will also be derived, where X = 7 days after the first vaccination on the Day 1, 8 and 30 regimen, and X = 14 after the second, third vaccinations on the Day 1, 8, and 30 regimen and after each vaccination on the Month 0, 1, and 6 regimen.

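### The SAP allows Grade 4 to be determined from an SAE report, so redness or swelling could be tabulated as Grade 4 without the findings that the grading scale requires

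*Protocol*

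**What the plan says.** **Who assigns Grade 4.** Protocol Section 7.1.1.2 states: "Only an investigator or medically qualified person is able to classify" a local reaction as Grade 4. SAP Section 3.5.3.1, under Maximum Severity for Local Reactions, repeats this.

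**What Grade 4 means.** Protocol Table 2 defines Grade 4 redness as "Necrosis or exfoliative dermatitis" and Grade 4 swelling as necrosis alone. SAP Table 5 carries the same definitions. Short of those findings, both items are graded by diameter: 2.5 to 5.0 cm is Grade 1, above 5.0 to 10.0 cm is Grade 2, and above 10 cm is Grade 3. For pain, an emergency room visit or an admission is itself the Grade 4 criterion.

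**The added route.** Directly after the restriction, the SAP says: "Grade 4 could also be determined if a reaction is reported as an SAE". The protocol has no matching sentence.

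**What makes an event an SAE.** Protocol Section 8.6 includes an event that "Requires inpatient hospitalization or prolongation of existing hospitalization". It also covers events judged medically important without admission: "the important medical event should be reported as serious". Under Section 8.1, "any nonserious AE that is determined by the sponsor to be serious will be reported by the sponsor as an SAE". None of these routes refers to a toxicity grade.

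**The concern.** Severity of local reactions is a primary safety endpoint (SAP Section 3.1.2), and Grade 4 is its worst category. The SAP sentence lets seriousness stand in for the clinical finding that defines the category. It also sits beside a restriction that it can contradict: where the sponsor upgrades an event to an SAE, a Grade 4 could appear that no investigator or medically qualified person had classified.

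Erythema is the sensitive item in this programme. The Protocol Summary reports that vaccinations in the preceding Phase 2 study were stopped after 7 cases of Grade 3 injection site erythema among 162 subjects given the second dose. A reader of the study report will therefore look closely at the upper rows of the erythema severity table. An entry there that rests on SAE status alone would misstate what was observed.

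**Working it through.** No stated sample size, power or error rate depends on this point, so there is no plan figure to reproduce. The check is a comparison of texts, followed by an illustration of size.

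**Step 1: apply both rules to the same reaction.**

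| Reaction | Table 2 / Table 5 | SAE sentence, read literally |
|---|---|---|
| Redness above 5.0 to 10.0 cm, admitted, no necrosis or exfoliative dermatitis | Grade 2 | Grade 4 |
| Swelling above 10 cm, reported as medically important, no necrosis | Grade 3 | Grade 4 |
| Redness 2.5 to 5.0 cm, made an SAE by the sponsor, no necrosis or exfoliative dermatitis | Grade 1 | Grade 4 |
| Redness with necrosis, admitted | Grade 4 | Grade 4 |
| Pain leading to admission | Grade 4 | Grade 4 |

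The rules agree in the last two rows and disagree in the first three. The disagreement is confined to redness and swelling that are SAEs without the defining finding.

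**Step 2: trace which outputs change.** SAP Section 3.5.3.1 derives the maximum severity of each local reaction. It also derives a daily variable for the presence of a Grade 3 or Grade 4 reaction.

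- Redness of 6 cm is 6 / 0.5 = 12 measuring device units, which falls in the Grade 2 band of 11 to 20. Under the literal rule it would enter the Grade 4 row and could also be added to the severe-or-greater variable.
- Redness above 10 cm is already Grade 3. Only the maximum-severity row would change.

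**Step 3: size.** SAP Section 6.5.2 specifies Clopper-Pearson 95% limits. Assume n = 183 in the denominator (the planned group size in Protocol Table 1) and no true Grade 4 reaction. With r cases counted as Grade 4, the lower limit is the 0.025 quantile of Beta(r, n − r + 1) and the upper limit is the 0.975 quantile of Beta(r + 1, n − r). This is equivalent to the F-distribution form in SAP Section 5.2.1.

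- r = 0: rate 0%. Upper limit 1 − 0.025^(1/183) = 0.0200, so 0% to 2.0%.
- r = 1: rate 1/183 = 0.55%. Lower limit 1 − 0.975^(1/183) = 0.00014; upper limit 0.0301. So 0.01% to 3.0%.
- r = 2: rate 2/183 = 1.09%. Limits 0.13% to 3.9%.

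These figures show what one or two such cases would do to the table. They do not estimate how likely a case is.

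**The case against.** **The sentence may only name a data source.** It says Grade 4 could be determined, not that it will be. The e-diary cannot yield Grade 4: the subject's pain categories stop at severe and the measuring device stops at 21+. Grade 4 must therefore come from elsewhere, and an SAE report is a sensible place to look. The sentence follows a restatement of the restriction, the same section names Table 5 as the scale, and SAEs are ordinarily reported by the investigator (Protocol Section 8.15.1). This reading is reasonable, and it is why the sentence should not simply be deleted: an SAE report is a proper source for Grade 4 pain. But the word also suggests a second route, the text requires no check against Table 5, and two programmers could code it differently.

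**Cases are unlikely.** This stands. Protocol Section 1.2.3 reports no actual severe or Grade 4 local reactions in Phase 1. The Grade 3 erythema cases in the preceding Phase 2 study all resolved, without accompanying severe systemic symptoms.

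**Wider readings that the documents do not support.**

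- A reader might extend the rule to vomiting and fever, because SAP Section 3.5.3.2 derives some systemic variables similarly to local reactions. That phrase introduces summaries after any vaccination. The SAE sentence is not repeated there, and it speaks of a reaction, where the SAP calls systemic items events. Grade 4 vomiting also has its own criterion, "Emergency room visit or hospitalization for hypotensive shock", so it is not wholly separate from hospital care.
- A reader might infer a false trigger of the safety review rule. Protocol Section 7.1.2 requires a confirmed Grade 4 erythema and is applied during the trial. It does not use the SAP derivation.
- A reader might take Protocol Section 8.9 as forbidding any mixing of the two concepts. It says "Note the distinction between the severity and the seriousness of an AE", but it concerns the intensity scale on the AE form. The solicited scales themselves use emergency care or admission as Grade 4 for several items.
- The restriction covers medically qualified persons as well as the investigator, so Grade 4 is not reserved to the investigator alone.

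**Conclusion.** The point holds for redness and swelling. As written, SAP Section 3.5.3.1 permits a Grade 4 entry on SAE status alone. That conflicts with the restriction stated just before it, with SAP Table 5 and with Protocol Table 2. Because it is a stated rule that can misgrade a reaction, and not merely a missing detail, it is worth correcting, but it is minor.

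The reach is two of the three solicited local reactions. The effect is confined to the maximum-severity summary and, where the diameter is below Grade 3, the severe-or-greater summary. One such case in 183 would turn 0% (0% to 2.0%) into 0.55% (0.01% to 3.0%). This assumes a literal reading of the SAP sentence, a full group of 183 in the denominator and no reaction that truly meets Grade 4. Trial conduct, including the Section 7.1.2 review rule, is unaffected. Whether the sentence was meant to reach systemic events cannot be settled from the text, so the SAP should say.

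**What to change.** Keep the SAE report as a source of information, but tie it to the scale. In SAP Section 3.5.3.1, replace the sentence with:

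*An SAE report supports Grade 4 only when it documents the Grade 4 criterion for that reaction in Table 5, as classified by an investigator or medically qualified person.*

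In SAP Section 3.5.3.2, add:

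*Systemic events are graded by Table 6 and not by SAE status alone.*

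The cost is one replaced sentence and one added sentence in the SAP. No new data, form or protocol change is needed. Legitimate Grade 4 pain remains identifiable from SAE reports.

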**Table 2. Local Reaction Grading Scale**

	Mild (Grade 1)	Moderate (Grade 2)	Severe (Grade 3)	Grade 4
Pain	Does not interfere with activity	Interferes with activity	Prevents daily activity	Emergency room visit or hospitalization
Erythema/ Redness	2.5 cm to 5.0 cm (5 to 10 measuring device units)	>5.0 cm to 10.0 cm (11 to 20 measuring device units)	>10 cm ( $\geq 21$ measuring device units)	Necrosis or exfoliative dermatitis
Induration/ Swelling	2.5 cm to 5.0 cm (5 to 10 measuring device units)	>5.0 cm to 10.0 cm (11 to 20 measuring device units)	>10 cm ( $\geq 21$ measuring device units)	Necrosis

#### 7.1.1.3. Systemic Events

During the e-diary reporting period, subjects will be asked to assess vomiting, diarrhea, headache, fatigue, new or worsening muscle pain, and new or worsening joint pain and to record the symptoms in the e-diary. The symptoms will be assessed by the subject as absent, mild, moderate, or severe according to the grading scale in [Table 3](#). Only an investigator or medically qualified person is able to classify a subject's systemic events as Grade 4. If a subject experiences a suspected Grade 4 systemic event, the investigator must immediately notify the sponsor. If a subject experiences a confirmed Grade 4 systemic event determined to be related to the administration of the investigational product, further vaccinations will be discontinued in that subject. Further, if a systemic event persists beyond the end of the e-diary period following vaccination, the subject will be requested to report that information and any new AEs that develop to the investigator. The investigator will enter this additional information in the CRF.

**Table 3. Systemic Event Grading Scale**

	Mild (Grade 1)	Moderate (Grade 2)	Severe (Grade 3)	Grade 4
Vomiting	1-2 times in 24 hours	>2 times in 24 hours	Requires IV hydration	Emergency room visit or hospitalization for hypotensive shock
Diarrhea	2-3 loose stools in 24 hours	4-5 loose stools in 24 hours	≥6 loose stools in 24 hours	Emergency room visit or hospitalization
Headache	No interference with activity	Some interference with activity	Significant; prevents daily activity	Emergency room visit or hospitalization
Fatigue/ Tiredness	No interference with activity	Some interference with activity	Significant; prevents daily activity	Emergency room visit or hospitalization
New or worsening muscle pain	No interference with activity	Some interference with activity	Significant; prevents daily activity	Emergency room visit or hospitalization
New or worsening joint pain	No interference with activity	Some interference with activity	Significant; prevents daily activity	Emergency room visit or hospitalization

Abbreviation: IV = intravenous.

#### 7.1.1.4. Fever

In order to record information on fever, a digital thermometer will be given to the subject with instructions on how to measure oral temperature at home. Temperature will be collected in the e-diary in the evening daily during the e-diary reporting period. It will also be collected at any time during the e-diary data collection periods that fever is suspected. If a fever persists beyond the end of the e-diary period following vaccination, the subject will be requested to report that information and any new AEs that develop to the investigator. The investigator will enter this additional information in the CRF. Fever is defined as an oral temperature of  $\geq 38.0^{\circ}\text{C}$  ( $100.4^{\circ}\text{F}$ ). The highest temperature for each day will be recorded in the e-diary. In the event of a fever, temperature will be collected daily until fever has resolved (1 day of temperature less than  $38.0^{\circ}\text{C}$  [ $100.4^{\circ}\text{F}$ ]). Temperature will be measured and recorded to 1 decimal place and then categorized during analysis according to the scale shown in Table 4.

**Table 4. Scale for Fever**

Mild (Grade 1)	38.0-38.4°C (100.4-101.1°F)
Moderate (Grade 2)	38.5-38.9°C (101.2-102.0°F)
Severe (Grade 3)	39.0-40.0°C (102.1-104.0°F)
Grade 4	>40.0°C ( $>104.0^{\circ}\text{F}$ )

If a subject experiences a confirmed Grade 4 fever determined to be related to the administration of the investigational product, further vaccinations will be discontinued in that subject.

### 7.1.2. Triggered Safety Data Review Rule

In light of the occurrence of cases of Grade 3 injection site erythema in subjects receiving a different formulation of the *C difficile* vaccine on a Day 1, 8, and 30 regimen (Section 1.2.3), a triggered safety data review rule will apply during the course of the study for e-diary-prompted injection site erythema. This is designed to trigger if the estimated lower limit of the 1-sided 97.5% CI around the rate of Grade 3 injection site erythema is greater than 2.1% among recipients of active vaccine.

The rule will be assessed in a blinded manner and will apply separately to each dose of vaccine (ie, Doses 1, 2, and 3) and each vaccination regimen (ie, Day 1, 8, and 30 or Month 0, 1, and 6), irrespective of vaccine allocation. The rule will not be applied to the fourth dose during the extension stage. E-diary data confirmed to be entered by the subject in error will not contribute towards the rule.

The triggered safety data review rule will have been met if 1 confirmed case of Grade 4 injection site erythema is reported. If more than 1 confirmed case of Grade 3 injection site erythema is reported, the rule will be assessed as follows. The number of confirmed cases (occurring after the specified dose number in the specified vaccination regimen) will be compared with the total number of subjects who have received the specified dose number in the specified vaccination regimen (in the knowledge that approximately 1 of 7 subjects will have received placebo). If the total number of subjects is less than or equal to the corresponding value shown in Table 5, the triggered safety data review rule will have been met.

**Table 5. Triggered Safety Data Review Rule Criteria for Grade 3 Injection Site Erythema After the Specified Dose Number in the Specified Vaccination Regimen**

Number of Confirmed Case(s) of Grade 3 Injection Site Erythema	Number of Subjects Having Received the Specified Dose Number in the Specified Vaccination Regimen
1	Rule does not apply
2	14
3	35
4	63
5	94
6	126
7	161
8	199
9	236
10	276
11	315
12	355
13	397
14	427

If the rule is met, the Pfizer IRC will conduct an expedited review of the available safety data in an unblinded manner to determine whether enrollment of new subjects to the impacted

vaccination regimen and administration of study injections to subjects already enrolled in the impacted vaccination regimen should be halted temporarily or whether any other measures should be taken to ensure subject safety. If the IRC determines that enrollment and vaccination in the impacted regimen should be halted temporarily, the data will also be reviewed by the E-DMC. Enrollment and vaccination of subjects in the impacted vaccination regimen will not recommence until the E-DMC evaluates all available safety data and provides recommendations and the sponsor notifies sites that these activities may continue (refer to [Section 9.5](#)). In the meantime, all other routine study conduct activities such as ongoing data entry, reporting of AEs, subject e-diary completion, and subject follow-up must continue. If only 1 vaccination regimen is impacted by the triggered safety data review rule, enrollment and vaccination in the other vaccination regimen will continue per protocol.

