### 3.4. Vaccine Groups and Enrollment

For the original portion of the study, subjects will be assigned to 1 of 6 study groups listed in Table 1. For each dosing regimen, approximately 366 subjects will receive the *C difficile* vaccine (at either 100 or 200 µg total toxoid dose level) and approximately 61 subjects will receive placebo (saline).

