#### **9.5. Data Monitoring Committee**

This study will utilize a Pfizer IRC, which will be responsible for reviewing data in the event the triggered safety data review rule is met and also to review the results of the 4 planned interim analyses. The IRC will be composed of senior Pfizer Vaccine Research & Development personnel, not directly involved with the study conduct, which serves to make recommendations based on safety findings or the results of the interim analyses. These could include advance ordering of future clinical trial supplies or an administrative increase in the number of subjects enrolled by a maximum of 30%.

In addition, the study will use an E-DMC independent of Pfizer. The E-DMC will be responsible for ongoing monitoring of the safety of subjects in the study, including review of unblinded data according to the charter. The E-DMC is scheduled to hold regular review meetings approximately twice a year to review safety results. Additional ad hoc E-DMC meetings will be held as needed. The recommendations made by the E-DMC to alter the conduct of the study will be forwarded to Pfizer for final decision. Pfizer will forward such decisions, which may include summaries of aggregate analyses of endpoint events and of safety data that are not endpoints, to regulatory authorities, as appropriate.

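### Table 5 of the Grade 3 erythema rule stops at 427 subjects, but Section 9.5 allows up to 30% more, and above 427 dosed in a regimen no Grade 3 count can meet the rule as written

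*Protocol*

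**What the plan says.** Protocol Section 7.1.2 applies the rule throughout the study. It states the design target as follows: the rule acts if the "estimated lower limit of the 1-sided 97.5% CI around the rate of Grade 3 injection site erythema is greater than 2.1" (per cent) among recipients of active vaccine. It "will apply separately to each dose of vaccine (ie, Doses 1, 2, and 3) and each vaccination regimen", and the count is made blind, on the understanding that "approximately 1 of 7 subjects will have received placebo".

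The working test is a table lookup. For two or more confirmed Grade 3 cases, the rule is met "If the total number of subjects is less than or equal to the corresponding value shown in Table 5". Table 5 runs from 2 cases (14 subjects) to 14 cases (427 subjects) and has no row for 15 or more. Separately, the rule "will have been met if 1 confirmed case of Grade 4 injection site erythema is reported".

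Section 3.4 sets the planned size: "For each dosing regimen, approximately 366 subjects will receive the" vaccine and about 61 placebo, so 427 per regimen and 854 in all. Section 9.5 says that the internal review committee's recommendations could include "an administrative increase in the number of subjects enrolled by a maximum of 30" (per cent).

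No section extends Table 5, gives a formula for larger numbers, or says what becomes of the rule after an increase. The SAP does not mention the rule.

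**The concern.** The lookup works only while the number dosed is no larger than some printed value, and the largest printed value is 427. Beyond that the condition is false for every row, and counts of 15 or more have no row. The stated target and the operating test then disagree: the lower limit can exceed 2.1% while the rule cannot be met.

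Grade 3 erythema is the reaction that stopped vaccinations in the sponsor's earlier Phase 2 study of a different formulation, and it is the reason given for the rule. What is at stake is whether this prespecified trigger for expedited unblinded review still covers subjects added under Section 9.5.

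Timing adds to the concern. The first interim analysis waits for Month 2 data from all continuing subjects (Section 9.4.1). Subjects added after it would receive Doses 1 and 2 when the number dosed is already at or near 427.

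**Working it through.** **Inputs.** Criterion, placebo fraction and Table 5: Section 7.1.2. Regimen size 366 + 61 = 427: Section 3.4. Total 854: Section 3.1. Increase of up to 30%: Section 9.5.

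**Step 1: reproduce Table 5.** For x cases among n active recipients, the exact (Clopper-Pearson) lower limit L is the 0.025 quantile of a beta distribution with parameters x and n − x + 1. For each x, take the largest n with L ≥ 2.05% (that is, L rounds to 2.1%), multiply by 7/6 to allow for placebo, and round up.

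- 2 cases: n = 12, and 12 × 7/6 = 14. Printed: 14.
- 7 cases: n = 138, and 138 × 7/6 = 161. Printed: 161.
- 13 cases: n = 340, and 340 × 7/6 = 396.7, rounded up to 397. Printed: 397.

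All 12 rows from 2 to 13 cases match exactly. Row 14 does not: n = 376 gives 438.7, rounded up to 439, against 427 printed. Since 427 is the planned regimen size, the last row looks like a cap at that size.

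This construction is inferred; the protocol does not state it. The text says greater than 2.1%. Read strictly, with active n taken as 6/7 of the total and rounded, the boundaries are mostly a little lower (13 cases: 387; 14 cases: 428).

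**Step 2: size after an increase.** 854 × 1.30 = 1110.2, about 1110 in total. 427 × 1.30 = 555.1, about 555 per regimen if split evenly. Section 9.5 does not say how extra subjects would be divided. If all 256 went to one regimen it would reach 427 + 256 = 683.

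**Step 3: compare criterion and lookup above 427** (active n = 6/7 of N, rounded).

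| Cases | N dosed | Active n | Lower limit | Exceeds 2.1%? | Can meet Table 5? |
|---|---|---|---|---|---|
| 14 | 427 | 366 | 2.107% | yes | yes |
| 15 | 440 | 377 | 2.24% | yes | no |
| 16 | 500 | 429 | 2.15% | yes | no |
| 17 | 555 | 476 | 2.09% | only after rounding | no |
| 18 | 555 | 476 | 2.26% | yes | no |
| 30 | 555 | 476 | 4.29% | yes | no |

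**Step 4: size of the loss.** Simulation of one dose in one regimen of 555, with 6 of 7 subjects active, no placebo cases, everyone receiving the dose, and the count checked continuously. The last column is the chance that the strict 2.1% criterion is first crossed between 428 and 555, where the table cannot register it.

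| True rate in active | Rule met by N = 427 | First crossing at 428 to 555 |
|---|---|---|
| 2.1% | about 12% | 0.8% |
| 3% | about 38% | 5.5% |
| 4% | about 73% | 7.7% |
| 5% | about 93% | 3.7% |

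Continuing the table on the rounded convention gives much the same loss. Printed against continued: 11.5% vs 12.4% at a true rate of 2.1%, 39% vs 45% at 3%, 58% vs 66% at 3.5%, 74% vs 82% at 4%, and 93% vs 97% at 5%. The differences are 0.9, 6, 8, 8 and 4 points.

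**The case against.** The strongest reply is that the trial as planned has no gap. Table 5 covers 427 per regimen in full. Section 9.5 lists the increase only as something a recommendation could include, and the sponsor could revise the table if the increase were taken up. That stands as a limit on scope. It does not remove the inconsistency: the increase is described as administrative, and nothing ties it to a revision of Table 5. Group sizes are also only approximate, so slight over-enrolment is enough to pass the last row.

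Other safeguards remain. A rule already met at or below 427 stays met. One Grade 4 case triggers at any number. A related, confirmed Grade 3 reaction ends vaccination in that subject. The external committee reviews unblinded safety data about twice a year and ad hoc. All of this stands and lowers the practical risk. None of it is the prespecified numerical trigger that Section 7.1.2 promises.

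The count is of subjects dosed, not enrolled. At the 12% maximum dropout of Section 9.1, used here as an upper-end loss before Dose 3, 427 dosed corresponds to 427 / 0.88 = about 485 enrolled. That narrows the gap for Dose 3 but does not close it, since 555 × 0.88 = 488 is still above 427.

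A reader might infer that the printed row 14 is wrong. The documents do not support that: 14 of 366 gives 2.107%, above the stated 2.1%, and 427 is within one subject of the strict boundary of 428. The figure of 439 follows only from the inferred rounding convention.

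**Conclusion.** The point holds, conditionally. If more than 427 subjects receive a given dose in a regimen, the Grade 3 part of the rule cannot be met on any count assessed from then on, although its stated criterion can be satisfied. The condition is that the Section 9.5 increase is used or a regimen over-enrols.

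The expected effect is modest: about 1 to 8 percentage points off the chance of triggering at 555 per regimen, for constant true rates of 2.1% to 5%. This rests on the even split and the simulation assumptions in the working.

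Two stronger readings should be set aside. One is that the rule is defective in the trial as planned; it is not, because the table is complete to 427. The other is that most of the protection would be lost. A large loss (67% down to 9%) appears only if the rate is supposed to jump from 2% in the first 427 subjects to 10% in the 128 added. Nothing in the documents suggests such a jump.

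This should be corrected because it concerns a stated safety rule in a scenario that the protocol allows, and correction is cheap.

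**What to change.** Reconcile Sections 7.1.2 and 9.5 so that the stated criterion can be applied at every regimen size that Section 9.5 permits, including an uneven split of added subjects.

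As part of this, the sponsor should confirm the convention behind Table 5. Rows 2 to 13 match a lower limit that rounds to 2.1%, while the text says greater than 2.1%. The choice matters above 427: at 555 subjects the criterion is reached at 17 cases on the first reading and 18 on the second. Any further rows should be derived by the sponsor from the confirmed convention. This review does not propose boundary values.

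The cost is a few table rows or one sentence in a protocol amendment, with no extra subjects or procedures. If the increase is used, slightly more reviews would be triggered at a true rate of 2.1% (12.4% against 11.5% on the rounded convention).
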